5.1.2.7 Duration of Response per iRECIST (iDOR)

iDOR is defined as the time from the date of the first response iCR/iPR (whichever is first recorded) to the date of radiographical progression or date of censoring. iDOR will be

calculated only for the subgroup of participants with confirmed response iCR/iPR per iRECIST separately for investigator assessment.

Table 4 iDOR Definition

iDOR		
Situation	Date of Event or Censor	Outcome
Participant did not receive new anti-cancer therapy		
iCPD	First date where iUPD criteria are met	Event
No iCPD nor death and NOT in one of the following cases : a) the participant stops protocol treatment because they were not judged to be clinically stable, b) no further response assessments are done (because of participant refusal, protocol non-compliance, or participant death); c) the next timepoint responses are all iUPD, and iCPD never occurs;	Date of last radiological assessment	Censor
No iCPD nor death and is in one of the following cases : a) the participant stops protocol treatment because they were not judged to be clinically stable, b) no further response assessments are done (because of participant refusal, protocol non-compliance, or participant death); c) the next timepoint responses are all iUPD, and iCPD never occurs;	First date where iUPD criteria are met	Event
Participant received new anti-cancer therapy		
No progression before new ACT	Date of last radiological assessment before start of new ACT	Censor
iCPD before new ACT	First date where iUPD criteria are met	Event
iUPD before new ACT and NOT in one of the following cases : a) the participant stops protocol treatment because they were not judged to be clinically stable, b) no further response assessments are done (because of participant refusal, protocol non-compliance, or participant death); c) the next timepoint responses are all iUPD, and iCPD never occurs;	Date of last radiological assessment before start of new ACT	Censor

iDOR		
Situation	Date of Event or Censor	Outcome
Participant did not receive new anti-cancer therapy		
iUPD before new ACT and is in one of the following cases : a) the participant stops protocol treatment because they were not judged to be clinically stable, b) no further response assessments are done (because of participant refusal, protocol non-compliance, or participant death); c) the next timepoint responses are all iUPD, and iCPD never occurs;	First date where iUPD criteria are met	Event
Missed >=2 scheduled radiological assessments		
If last assessment prior to missing >= 2 scans is iUPD	First date where iUPD criteria are met	Event
If last assessment prior to missing >= 2 scans is not iUPD and no progression after missing >=2 scans	Date of last radiological assessment	Censor
If radiographical progression occurs after missing 2 scheduled radiological assessments and last assessment prior to missing >= 2 scans is not iUPD	Date of last radiological assessment before missing 2 scans	Censor

iDOR = Date of Event or Censor – Date of First iCR/iPR +1

Missing 2 scheduled imaging assessments:

Missing 2 scheduled imaging assessments is defined as the gap between two imaging assessments being more than 140 days (2.5 times the scheduled imaging assessment interval (2.5 x 56 days)). Imaging assessments after first iUPD will be excluded in DOR derivation.

Note: Participant cannot be censored at “NE”. If NE is the only previous assessment, then DOR/iDOR will be censored at Day 1.

To apply the cut-off date to DOR/iDOR is to exclude those tumor assessments after cut-off date and anti-cancer therapy date after cut-off date in the analysis.

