7.1 Efficacy Assessments

Disease response and progression will be evaluated in this study using the RECIST v1.1 and iRECIST criteria as assessed by independent central review and investigator.

Tumor assessments will be performed at screening and at every 8 weeks (\pm 1 week) from C1D1 until confirmed disease progression by iRECIST (iCPD). Scans will be read on site and also submitted in digital format for independent central review. Procedures for independent imaging central review will be described in a separate imaging charter. The assessment will include tumor measurements for target lesions, non-target lesions, and assessment for any new lesions. An overall assessment will be characterized for time point evaluation.

Computed tomography (CT) or magnetic resonance imaging (MRI) scans are preferred for this study and to ensure comparability, the same technique (CT/MRI) used at screening should be utilized throughout the study. The same method should be employed and assessed by the same individual on each occasion, when possible. Imaging should include chest, abdomen and pelvis as well as any other anatomical region appropriate for the participant's disease.

Imaging should be done every 8 weeks from C1D1 regardless of treatment interruption or delays and through the follow-up period as applicable. Scans performed prior to informed consent as standard of care are acceptable as screening scans if done within 28 days prior to C1D1. If a biopsy of a target lesion is performed, the baseline scan should be repeated, if possible.

Confirmatory scans for CR or PR should be done at least 4 weeks after the date of the scan that CR or PR was first observed. Confirmatory scans for PD must occur at least 4 weeks after the date of the scan that PD was first observed but no longer than 8 weeks.

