5.1.2.5 Progression-free Survival per iRECIST (iPFS)

iPFS is defined as the time from the start of the study treatment until death from any cause or radiographic disease progression assessed per iRECIST by investigator assessment, whichever occurs first.

If iUPD occurs but iSD, iPR, or iCR is observed any time subsequent to iUPD, iUPD status will be disregarded for determination of iPFS.

Table 2 iPFS Definition

iPFS		
Situation	Date of Event or Censor	Outcome
No evaluable post-baseline imaging assessments, no death	Date of first dose (Day 1)	Censor
Participant did not receive new anti-cancer therapy:		
iCPD	First date where iUPD criteria are met	Event
No iCPD, but death recorded on eCRF	Date of death	Event
No iCPD nor death and not in one of the following cases :a)if the participant stops protocol treatment because they were not judged to be clinically stable, b) no further response assessments are done (because of participant refusal, protocol non-compliance, or participant death); c) the	Date of last radiological assessment	Censor

iPFS		
Situation	Date of Event or Censor	Outcome
next timepoint responses are all iUPD, and iCPD never occurs;		
No iCPD nor death and is in one of the following cases : a)if the participant stops protocol treatment because they were not judged to be clinically stable, b) no further response assessments are done (because of participant refusal, protocol non-compliance, or participant death); c) the next timepoint responses are all iUPD, and iCPD never occurs;	First date where iUPD criteria are met	Event
Participant received new anti-cancer (ACT) therapy:		
No progression before new ACT	Date of last radiological assessment before start of new anti-cancer therapy	Censor
iCPD before new ACT	First date where iUPD criteria are met	Event
iUPD before new ACT and not in one of the following cases : a)if the participant stops protocol treatment because they were not judged to be clinically stable, b) no further response assessments are done (because of participant refusal, protocol non-compliance, or participant death); c) the next timepoint responses are all iUPD, and iCPD never occurs;	Date of last radiological assessment before start of new anti-cancer therapy	Censor

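### SAP 5.1.2.7 dates iDOR events at an unqualified first iUPD, so a confirmed responder with an earlier or transient iUPD who later has an event gets a wrong duration

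*SAP*

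**What the plan says.** - **Start of the clock.** SAP 5.1.2.7 starts iDOR at the first recorded iCR or iPR, for confirmed responders only. The formula under Table 4 subtracts "Date of First iCR/iPR +1" from the event or censoring date.
- **Event date.** Five rows of Table 4 give the event date as "First date where iUPD criteria are met". They are: iCPD without new anticancer therapy; an iUPD left standing without new therapy; the same two situations before new therapy; and an iUPD as the last assessment before two or more missed scans. No row says that the iUPD must come after the response, or that it must be the one later confirmed.
- **Reset rule.** SAP 5.1.2.5 says: "If iUPD occurs but iSD, iPR, or iCR is observed any time subsequent to iUPD, iUPD status will be disregarded for determination of iPFS". Section 5.1.2.7 has no counterpart.
- **Exclusion sentence.** Section 5.1.2.7 states: "Imaging assessments after first iUPD will be excluded in DOR derivation".
- **Scans.** Protocol 7.1 says: "Imaging should be done every 8 weeks from C1D1 regardless of treatment interruption or delays". Assessment continues until iCPD.
- **Output.** SAP 6.4.2.7 plans a listing of iDOR and nothing else.

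**The concern.** iDOR should run from response to the progression that ends it. The table ties the end date to the first iUPD without qualification, and the only rule that cancels a superseded iUPD is confined to another endpoint. Two patterns then go wrong if the participant later reaches an event row:

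- An iUPD **before** the response puts the event date ahead of the start date, so the duration is negative.
- A transient iUPD **during** the response ends the duration at an episode that was later reversed. The value is positive and plausible, but too short.

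The SAP allows for such sequences. Scanning continues past iUPD, clinically stable participants with iUPD may enter the Observation Period (Protocol 4.1.2), and the reset sentence in 5.1.2.5 provides for iPR or iCR after iUPD. At stake are individual values in the iDOR listing, and agreement between iDOR and iPFS on when a participant progressed.

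**Working it through.** The plan gives no iDOR figure to reproduce, so I applied its formula to example scan sequences.

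**Inputs.** Scans every 56 days from Day 1 (Protocol 7.1) fall on Days 57, 113, 169, 225, 281 and 337. The formula is iDOR = event or censoring date - date of first iCR/iPR + 1 (SAP 5.1.2.7). The response sequences are illustrative assumptions. In every case the response is confirmed on a later scan.

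**Two readings.** *As written* uses the first iUPD in the record. *With reset* uses the first iUPD not followed by iSD, iPR or iCR, which is the 5.1.2.5 rule carried over to iDOR.

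| Sequence | As written | With reset |
|---|---|---|
| A. iUPD 57, iPR 113, iPR 169, iUPD 225, iCPD 281 | 57 - 113 + 1 = -55 | 225 - 113 + 1 = 113 |
| B. iUPD 57, iSD 113, iPR 169, iPR 225, iUPD 281, iCPD 337 | 57 - 169 + 1 = -111 | 281 - 169 + 1 = 113 |
| C. iPR 57, iUPD 113, iPR 169, iPR 225, iUPD 281, iCPD 337 | 113 - 57 + 1 = 57 | 281 - 57 + 1 = 225 |
| D. iPR 57, iPR 113, iUPD 169, iCPD 225 | 169 - 57 + 1 = 113 | 169 - 57 + 1 = 113 |
| E. iUPD 57, iPR 113, iPR 169, iPR 225, no later progression | censored: 225 - 113 + 1 = 113 | censored: 113 |

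**What the rows show**

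1. A and B: an earlier iUPD makes iDOR negative once an event row applies. The sign is negative whenever the first iUPD precedes the first response by at least 2 days.
2. C: the error is a loss of 225 - 57 = 168 days, with nothing in the value to flag it. Taking the first iUPD *after* response does not repair this case; only a reset does. The row assumes that the clock starts at the first recorded iPR, Day 57.
3. D: with no superseded iUPD, the two readings agree.
4. E: a censored responder is unaffected. If scans after the first iUPD are also excluded, the last usable scan is Day 57, and the value becomes 57 - 113 + 1 = -55.

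**Comparison with iPFS in A.** With its reset, iPFS dates progression at Day 225. Table 4 read literally dates the same progression at Day 57.

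**The case against.** The strongest reply is that the narrative definition in 5.1.2.7 already describes an interval from first response to radiographic progression, which implies that progression comes second. Table 2 for iPFS uses the same event-date phrase, and there the reset makes clear that an overridden iUPD is not the progression date. A sensible programmer would carry one progression date into both endpoints. This has force: the SAP does not mandate negative durations, and the wrong values follow only from a literal reading. It does not close the gap, because the SAP states a reset and limits it to iPFS, and the order implied by the narrative does not rescue sequence C.

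The exclusion sentence refers to DOR, while neighbouring notes in 5.1.2.7 say DOR/iDOR. It may therefore be meant only for RECIST v1.1. That is possible, but it sits in the iDOR section and its scope is not stated.

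On consequence, iDOR is only listed, a negative entry would be seen, and no primary endpoint, dose decision or cohort-opening rule uses it. Swimmer plots (SAP 6.4) and the iPFS listing carry overlapping information. All of this stands and limits the weight of the point.

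A reader might infer that every response following an early iUPD gets a negative duration. Table 4 does not support that: the iUPD date applies only in event rows (sequence E). Nor do the documents support saying that durability becomes unreadable, given the other outputs.

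**Conclusion.** The point holds in a limited form. Under a literal reading of Table 4, a confirmed responder with an earlier or transient iUPD who later falls in an event row gets a wrong iDOR: -55 instead of 113 days in one illustration, 57 instead of 225 in another. Responders censored without progression are not affected unless the exclusion sentence is applied to iDOR.

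The scan days are assumed. They show direction and possible size, not frequency. The documents do not say how many confirmed responders there are or how many had a superseded iUPD, so the number affected is unknown and, after early closure, may be small. The effect is confined to the iDOR listing. It is still worth correcting: that listing is the only planned iDOR output, each value will be read individually, and an error of the sequence C kind would not be noticed.

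**What to change.** 1. In all five event rows of Table 4, define the event date as the first date iUPD criteria are met after the first iCR/iPR and not followed by iSD, iPR or iCR.
2. Extend the reset sentence in 5.1.2.5 to cover iDOR, or repeat it in 5.1.2.7.
3. Delete or reconcile the sentence in 5.1.2.7 that excludes imaging after the first iUPD. If it is left in place, it contradicts the reset, which needs those later scans. The similar sentence under Table 2 has the same conflict with the iPFS reset and should be settled at the same time.
4. State how the missed-scan row applies when a response follows the gap, since that row calls an event while the reset would cancel the iUPD.

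The cost is a few lines of SAP text and one derivation, with no new data. SAP Section 1 provides for approval of the final SAP before database hardlock and for documenting changes that affect the analyses in the CSR, so there is a route for the correction.

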5.1.2.8 Duration of Response per RECIST v1.1 (DOR)

DOR is defined as the time from the date of the first response CR/PR (whichever is first recorded) to the date of radiographical progression or date of censoring. DOR will be calculated only for the subgroup of participants with confirmed response CR/PR per RECIST v1.1, separately for investigator assessment.

Table 5 DOR Definition

DOR		
Situation	Date of Event or Censor	Outcome
Participant did not receive new anti-cancer therapy		
Radiographical progression documented per RECIST v1.1	Date of radiological PD	Event
No radiographical progression	Date of last radiological assessment	Censor
Participant received new anti-cancer therapy		
Radiographical progression documented per RECIST v1.1 after new ACT	Date of last radiological assessment before start of new anti-cancer therapy	Censor
Radiographical progression documented per RECIST v1.1 before new ACT	Date of radiological PD	Event
No radiographical progression	Date of last radiological assessment before start of new anti-cancer therapy	Censor
Missed >=2 scheduled radiological assessments		
If radiographical progression or death occurs after missing 2 scheduled radiological assessments	Date of last radiological assessment before missing 2 scans	Censor

DOE = Date of Event or Censor – Date of First CR/PR +1

Missing 2 scheduled imaging assessments:

Missing 2 scheduled imaging assessments is defined as the gap between two imaging assessments being more than 140 days (2.5 times the scheduled imaging assessment interval (2.5 x 56 days)).

5.2 Safety Endpoints

Safety and tolerability (determine MTD) are the primary endpoints of the study. Safety endpoints are adverse events (AEs), laboratory measurements, vital signs, physical examination and ECOG performance status (PS). Safety will be assessed by evaluation of the following variables:

5.2.1.1 Dose-Limiting Toxicity (DLT)

A DLT is defined as any of the listed events that occur within 28 days starting with the first dose on cycle 1 day 1 (C1D1) and that is considered to be related to IP. Confirmation of DLTs will be made by the DESC. The severity of AEs will be assessed according to the

National Cancer Institute's Common Terminology Criteria for Adverse Events (NCI-CTCAE).

5.2.1.2 ASP7517 Monotherapy Arm Dose-Limiting Toxicities (DLTs)

For participants in the ASP7517 monotherapy DLT is defined in the protocol in section 4.1.

5.2.1.3 ASP7517 and Pembrolizumab Combination Therapy Arm Dose-Limiting Toxicities (DLTs)

For participants in the ASP7517 and Pembrolizumab combination therapy arm, DLT is defined in the protocol in section 4.1.

Participants who are tolerating IP at a dose level that is being reviewed due to the occurrence of DLTs in another participant will not be automatically precluded from continued dosing during the safety review, and will be allowed to continue dosing for as long as tolerated unless directed otherwise as a result of the safety review by the DESC.

Dose escalation within individual participants will not be allowed.

5.2.1.4 Maximum Tolerated Dose (MTD) and Recommended Phase 2 Dose (RP2D)

Maximum Tolerated Dose

The MTD determination will be based on at least 6 evaluable participants at that dose level based on the BOPIN design. Based on the observed DLT(s) during the DLT observation period, the MTD is the highest dose for which the isotonic estimate of the DLT rate is closest to, but not over, the target DLT rate of 0.30 for monotherapy and combination therapy.

The dose level determined to be the MTD must have data from at least 6 participants.

Determination of MTD will be done for monotherapy and combination therapy separately.

Recommended Phase 2 Dose

The sponsor, in conjunction with the DESC, will determine the RP2D of ASP7517 as a single agent and in combination with pembrolizumab taking into consideration the safety and efficacy data, as well as other available data, such as pharmacokinetics and pharmacodynamics of ASP7517. The RP2D will not exceed the MTD.

The dose level determined to be the RP2D must have data from at least 6 participants.

Determination of RP2D will be done for monotherapy and combination therapy separately.

5.2.1.5 Adverse Events (AEs)

AEs will be coded using MedDRA v26.0 and graded using NCI CTCAE.

A treatment-emergent adverse event (TEAE) is defined as an AE observed after starting administration of the IP and 30 days after the final administration of IP. An IP-related TEAE is defined as any TEAE with at least possible relationship (possibly or probably related) to study treatment as assessed by the investigator or with missing assessment of the causal relationship.

The number and percentage of participants with TEAEs, IP-related TEAEs, serious TEAEs, IP-related serious TEASs, TEAEs leading to withdrawal of treatment and IP related TEAEs leading to withdrawal of treatment will be summarized by SOC, preferred term and treatment group. The number and percentage of TEAEs by severity will also be summarized. The worst severity will be summarized if the same AE is recorded more than once for a participant. If an AE is observed with different relationships to study drug then the AE will be counted under its maximum relationship only. In case the AE relationship is not reported, it will be treated as the maximum relationship.

If the adverse event occurs on Day 1 and the onset check box is marked “Onset after first dose of study IP” or the onset check box is left blank, then the adverse event will be considered treatment emergent. If the adverse event occurs on Day 1 and the onset check box is marked “Onset before first dose of study IP”, then the adverse event will not be considered treatment emergent. If a participant experiences an event both during the preinvestigational period and during the investigational period, the event will be considered as TEAE only if it has worsened in severity (i.e. it is reported with a new start date). All adverse events collected that begin within 30 days after taking the last dose of study IP will also be counted as TEAE.

Immune-related AE (irAE) and infusion related reactions (IRR) will be considered as Adverse Events of Special Interest (AEsi). The list of events classified as AEsi may change during the study due to ongoing pharmacovigilance.

Time to first onset of irAE will follow the following algorithm:

Situation	Date of Event or Censor	Outcome
AE of interest observed	Date of first onset	Event
No AE of interest observed and treatment ongoing	Date of data cutoff	Censor
No AE of interest observed and treatment discontinued	Date of last dose + 30 days	Censor

Time to First Onset = Date of Event or Censor – Date of First Dose +1

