9.4.3.1 Adverse Events

AEs will be coded using MedDRA and graded using NCI-CTCAE v5.0.

A TEAE is defined as an AE observed after starting administration of the IP until 30 days after the final administration of IP. An IP-related TEAE is defined as any TEAE with a causal relationship assessed as “yes” by the investigator.

The number and percentage of participants with TEAEs, drug-related TEAEs, serious TEAEs, drug-related serious TEASs, TEAEs leading to withdrawal of treatment and drug related TEAEs leading to withdrawal of treatment will be summarized by SOC, preferred term and treatment group. The number and percentage of TEAEs by severity will also be summarized. The worst severity will be summarized if the same AE is recorded more than once for a participant.

AE data will be listed.

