10.10 Appendix 10: Dose Modification and Toxicity Management for Immune-related AEs

AEs associated with pembrolizumab exposure may represent an immune-related response. These irAEs may occur shortly after the first dose or several months after the last dose of pembrolizumab treatment and may affect more than one body system simultaneously. Therefore, early recognition and initiation of treatment is critical to reduce complications. Based on existing clinical study data, most irAEs were reversible and could be managed with interruptions of pembrolizumab, administration of corticosteroids and/or other supportive care. For suspected irAEs, ensure adequate evaluation to confirm etiology or exclude other causes. Additional procedures or tests such as bronchoscopy, endoscopy, skin biopsy may be included as part of the evaluation. Dose modification and toxicity management guidelines for irAEs associated with pembrolizumab are provided in Table 17.

Based on the mechanism of action of ASP7517, immune-related adverse reactions (e.g., fever, headache, fatigue, hot flashes, diarrhea and muscular and joint pain) should be considered (see [Section 2.3.1.8 Other]) and managed as required per standard of care. In case of such events, ensure adequate evaluation to confirm etiology or exclude other causes. In addition, the study medical monitor should be contacted to discuss event monitoring, follow up and study treatment management.

Table 17 Dose Modification and Toxicity Management Guidelines for Immune-related Adverse Events Associated with Pembrolizumab

General instructions:

1. Severe and life-threatening immune-related adverse events (irAEs) should be treated with intravenous corticosteroids followed by oral steroids. Other immunosuppressive treatment should begin if the irAEs are not controlled by corticosteroids.
2. Pembrolizumab must be permanently discontinued if the irAE does not resolve or the corticosteroid dose is not ≤ 10 mg/day within 12 weeks of the last pembrolizumab treatment.
3. The corticosteroid taper should begin when the irAE is \leq Grade 1 and continue at least 4 weeks.
4. If pembrolizumab has been withheld, pembrolizumab may resume after the irAE decreased to \leq Grade 1 after corticosteroid taper.

Table continued on next page

irAEs	Toxicity grade (CTCAE v5.0)	Action with pembrolizumab	Corticosteroid and/or other therapies	Monitoring and follow-up

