6.5.2 Adverse Events

For the purpose of safety assessments in this study, events recorded during the pre-investigational period will be classified as Baseline Signs and Symptoms. All adverse events (AE) recorded on treatment including within 30 days from the last study treatment and serious adverse events (SAEs) on treatment including within 90 days of the last study treatment will be summarized.

Summaries and listings of SAEs and Serious TEAEs include SAEs upgraded by the sponsor based on review of the Sponsor's list of Always Serious terms if any upgrade was done.

The coding dictionary for this study will be MedDRA v26.0. It will be used to summarize AEs by SOC and PT. AEs will be graded using National Cancer Institute's Common Terminology Criteria for AEs (NCI-CTCAE).

An overview table will include the following details by dose level, phase, tumor type, and overall:

- Number and percentage of participants with TEAEs
- Number and percentage of participants with IP related TEAEs
- Number and percentage of participants with TEAE leading to death
- Number and percentage of participants with IP-related TEAE leading to death
- Number and percentage of participants with serious TEAEs and Astellas upgraded serious TEAE
- Number and percentage of participants with serious IP related TEAEs and Astellas upgraded serious IP related TEAE
- Number and percentage of participants with TEAEs leading to permanent discontinuation of study IP
- Number and percentage of participants with IP related TEAEs leading to permanent discontinuation of study IP
- Number and percentage of participants with CTCAE grade 3 or higher TEAE
- Number and percentage of participants with CTCAE grade 3 or higher IP related TEAE

The number and percentage of participants with TEAEs, as classified by SOC and PT will be summarized by dose level, phase, tumor type, and overall. Summaries will be provided for:

- DLTs within the DLT observation period
- TEAEs
- Deaths
- IP related TEAEs
- Serious TEAEs and Astellas upgraded serious TEAE
- IP related serious TEAEs and IP related Astellas upgraded serious TEAE
- TEAEs leading to permanent discontinuation of study IP
- IP related TEAEs leading to permanent discontinuation of study IP
- CTCAE Grade 3 or higher TEAEs
- IP-related CTCAE Grade 3 or higher TEAEs
- TEAEs excluding serious adverse events that equal to or exceed a threshold of 5% in any dose level
- common TEAEs that equal to or exceed a threshold of 5% in any dose level

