- Late SAEs occurring beyond 30 days from last study treatment

The number and percentage of participants with TEAEs, and TEAEs leading to death, as classified by PT only, will be summarized by dose level, phase, tumor type, and overall.

AE summary tables will include participant counts as opposed to AE counts. If a participant experiences more than one episode of a particular AE, that participant will be counted only once for that event. If a participant has more than one AE that code to the same preferred term, the participant will be counted only once for that preferred term. Similarly, if a participant has more than one AE within a body system, the participant will be counted only once in that body system.

The number and percentage of participants with TEAEs, as classified by SOC and PT will also be summarized by NCI-CTCAE severity grade, and by relationship to study drug. In the participant count, if a participant has multiple TEAEs with the same SOC or PT, but with differing severity grade or relationship, then the participant will be counted only once with the worst severity grade and highest degree of relationship, however, if any of the severity grade or relationship values are missing then the participant will be counted only once with missing severity grade or relationship.

The number and percentage of participants with TEAEs, as classified by SOC and PT will be summarized by dose level for SAF.

All AEs, deaths, SAEs, withdrawals due to adverse events, and AEs for re-screened participants will be displayed in listings.

The list of adverse events to be summarized may change during the course of the study due to ongoing pharmacovigilance.

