6.5.3 Adverse Events of Special Interest (AEsi)

The number and percentage of participants with Adverse Events of Special Interest (AEsi) such as IRR, irAE, and as classified by SOC and PT, will be summarized by dose level, phase, tumor type, and overall.

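### The irAE table has no window of its own; on the natural reading of the SAP, non-serious irAEs starting 31 to 90 days after the last dose are only listed

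*SAP*

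**What the plan says.** **Treatment-emergent window.** The two documents agree. Protocol 9.4.3.1: "A TEAE is defined as an AE observed after starting administration of the IP until 30 days after the final administration of IP". SAP 5.2.1.5: "All adverse events collected that begin within 30 days after taking the last dose of study IP will also be counted as TEAE".

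**What is summarized.** SAP 6.5.2 sets 30 days for adverse events in general, "All adverse events (AE) recorded on treatment including within 30 days from the last study treatment", and a longer period for serious ones: "serious adverse events (SAEs) on treatment including within 90 days of the last study treatment will be summarized". It also asks for a summary by system organ class and preferred term of "Late SAEs occurring beyond 30 days from last study treatment". Listings are not cut off: "All AEs, deaths, SAEs, withdrawals due to adverse events, and AEs for re-screened participants will be displayed in listings".

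**The irAE table.** SAP 6.5.3 asks for "The number and percentage of participants with Adverse Events of Special Interest (AEsi) such as IRR, irAE, and as classified by SOC and PT", by dose level, phase, tumor type and overall. It does not restrict the table to treatment-emergent events and gives no start or end date.

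**Collection.** Protocol 4.1.1 and 7.3.1, with Tables 3 and 4, collect adverse events at safety visits 30, 60 and 90 days after the last dose. Observation-period visits also include an adverse event assessment.

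**Timing of irAEs.** Protocol Appendix 10 (10.10): "These irAEs may occur shortly after the first dose or several months after the last dose of pembrolizumab treatment".

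**A leftover rule.** SAP 5.2.1.5 still carries a time-to-first-irAE algorithm that censors event-free participants who have stopped treatment at last dose + 30 days. The revision history in SAP Section 7 records that version 2.0 dropped this analysis.

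**The concern.** Safety and tolerability is a primary endpoint, and irAEs are the events of special interest. Protocol 2.3.1.9 notes that overlapping immune therapy could raise the rate of irAEs, so their proportion in the combination arm is a main safety output. The protocol expects that some may surface months after pembrolizumab ends, and it schedules visits that would record those arising up to day 90. If the summary stops at day 30, a non-serious irAE first seen at the 60- or 90-day visit is recorded but not counted in the irAE proportion. Protocol Table 17 shows that this need not be rare in kind: some irAEs, such as hypothyroidism, are handled while pembrolizumab continues and need not be serious.

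At stake is the completeness of a descriptive safety table. No hypothesis test, stopping rule or dose decision uses it.

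**Working it through.** The documents give no irAE rate, onset distribution or precision target for irAEs, so there is no planned figure to reproduce. The check compares windows, does day arithmetic on the planned schedule, and adds an illustration on assumed values.

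**1. Which events reach a summary table (30-day reading of SAP 6.5.3)**

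| Onset after last dose | Serious | Non-serious |
|---|---|---|
| Days 0–30 | Treatment-emergent tables | Treatment-emergent tables |
| Days 31–90 | 90-day SAE summaries and late-SAE table | Listings only |

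Non-serious events in the uncovered period: 90 − 30 = 60 days, and 60/90 = 67% of the off-treatment safety follow-up.

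**2. The window against the pembrolizumab interval**

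Inputs: ASP7517 every 28 days for six doses, on days 1, 29, 57, 85, 113 and 141. Pembrolizumab every 42 days, on days 1, 43, 85 and 127 in the Treatment period. Protocol Table 9 lists both as investigational product, so the 30-day clock starts at the last dose of either.

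- *Pembrolizumab given at the last dosing* (stopping after C1D1, C2D15, C4D1 or C5D15, or after any Observation Period dose): the window covers 30 of 42 days and leaves 42 − 30 = 12 days (12/42 = 29%) uncovered. After dose 17, given on day 1 + 16 × 42 = 673, it closes on day 703; the 90-day visit is on day 763.
- *All six cycles completed, then stop*: the last product is ASP7517 on day 141, so the window closes on day 171. That is 171 − 127 = 44 days after the last pembrolizumab dose, so the 42-day interval is covered. The 90-day visit is on day 231, which is 104 days after that dose.
- *Stopping earlier after an ASP7517-only dose* (day 29, 57 or 113): the window closes 58, 44 or 58 days after the last pembrolizumab dose (29 + 30 − 1, 57 + 30 − 43, 113 + 30 − 85).

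The shortfall against the dosing interval therefore depends on which product was given last.

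**3. Possible size, on assumed values only**

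Let s be the share of participants with an irAE by day 90 whose first one starts on days 31–90, and f the fraction of those whose event is serious. The share absent from every adverse event summary table is s × (1 − f).

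- s = 5%, f = 50%: 0.05 × 0.5 = 2.5%
- s = 20%, f = 0: 20%
- f = 100%: 0, whatever s is

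For the 12 combination participants planned in phase 1 (Protocol 9.2), let q be the assumed probability that a participant's only irAE is non-serious and starts on days 31–90. The expected number missed is 12q, and P(at least one missed) = 1 − (1 − q)^12.

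| q (assumed) | Expected missed | P(at least one) |
|---|---|---|
| 1% | 0.12 | 0.11 |
| 2% | 0.24 | 0.22 |
| 5% | 0.60 | 0.46 |
| 10% | 1.20 | 0.72 |

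One missed participant of 12 moves the proportion by 1/12 = 8.3 percentage points.

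**The case against.** **The 30-day sentences do not govern the irAE table.** One defines treatment-emergent events and the other opens SAP 6.5.2, while SAP 6.5.3 stands separately and omits the term that labels most of the 6.5.2 tables. A reader might infer that the SAP states a 30-day cut for irAEs; it does not. This stands, and the limit is an inference. It is still the natural one: 6.5.2 speaks of adverse events without exception, and 5.2.1.5 defines the events of special interest beside the 30-day rule. If the table is instead meant to include everything recorded, its counting period is undefined, because observation-period visits also collect events. Either reading calls for the same edit.

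**The leftover irAE algorithm does not cap events.** It counts an observed irAE at first onset; 30 days is only the censoring date for those without one. This is correct, so the rule is weak support for the inference. It is a reason to delete the text.

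**Late events are partly covered elsewhere.** Serious ones are in the 90-day summaries and the late-SAE table, and all events are listed. Laboratory shift tables (SAP 6.5.4) and liver thresholds (SAP 6.5.4.1) state no 30-day limit, so late hepatic changes may show there. For participants continuing pembrolizumab, Protocol Table 4 schedules the thyroid panel at the 30-day visit but not at 60 or 90 days, which limits what a longer window would find. All of this stands and narrows the point to non-serious events. But the late-SAE table does not identify irAEs, and laboratory tables do not count them.

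**No bias is shown, and little depends on the table.** A proportion reported for a declared window is not biased for that window. Dose decisions rest on 28-day DLTs, with delayed DLTs also considered (Protocol 2.3.2). The study closed early, and with few participants the listing can be read by eye. This stands as to severity. It does not make 30 days the better window for events the protocol itself expects may be late.

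**Conclusion.** The point holds in a limited form. On the natural reading of SAP 6.5.2 and 6.5.3, non-serious irAEs with onset on days 31–90 after the last dose have no adverse event summary table. Leaving them out can only lower the tabulated proportion with an irAE by day 90, or leave it unchanged. The size is unknown: the 2.5% to 20% range and the 12-participant illustration rest on assumed shares.

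Three stronger conclusions are tempting and unsupported. The first is that the irAE rate is in fact understated: the protocol says irAEs may occur late, and no late rate is given. The second is that two-thirds of late irAEs are lost: 67% is a share of days, and serious events are summarized. The third is that the window always falls short of the pembrolizumab interval: that happens only when pembrolizumab is given at the last dosing.

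This is an inexpensive improvement to a primary safety output. It does not call the safety analysis into question.

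**What to change.** In SAP 6.5.3, state the window and tabulate irAEs, serious and non-serious, with onset from first dose to 90 days after the last dose of any study drug, or to the start of new anticancer therapy if earlier. Present this beside the 30-day treatment-emergent tables, which stay as they are and remain consistent with Protocol 9.4.3.1. In SAP 5.2.1.5, delete the time-to-first-irAE algorithm with its last dose + 30 days censoring, since version 2.0 dropped that analysis.

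The cost is one changed window in one set of tables, using data already collected at the 30-, 60- and 90-day visits. A few late background events unrelated to treatment will be counted. Keeping the 30-day tables alongside lets the reader see how many irAEs the longer window adds.
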